4.2 Schedule

PROTOCOL SUMMARY/SCHEMA

SCHEDULE OF EVALUATIONS / STUDY CALENDAR

Parameter	Pre-study	Weekly *****	Before Each Cycle	Before Every 2 - 4 Cycles	Study Termination	Follow - Up
History	X				X	X
Physical examination	X		X	X	X	X
BP**	X	X	X	X	X	X
Weight	X		X	X	X	X
Measurement of extramedullary tumor*****	X		X	X	X	X
Performance status	X		X	X	X	X
CBC, differential, platelet count	X	X	X	X	X	X
Serum Chemistries (must include, Bilirubin, Alk Phos, ALT orAST)	X	X	X	X	X	X
Glucose and Electrolytes (Na, K, Cl, CO ₂)	X	X	X	X	X	X
PT/PTT/INR***	X		X	X	X	X
Bone marrow exam with cytogenetics and molecular studies for FLT3 and NPM1****	X			X	X	
Beta HCG	X					
Chest x-ray	X					
Brain CT or MRI scan *	X					

As appropriate

*Brain imaging (CT/MRI) should be performed only in patients with neurological signs and symptoms concerning for intracranial metastatic masses.

**Blood pressure should be monitored weekly during the first 4 weeks of sorafenib therapy and thereafter monitored and treated, if required, in accordance with standard medical practice. In cases of severe or persistent hypertension, despite institution of antihypertensive therapy, temporary or permanent discontinuation of sorafenib should be considered.

***Infrequent bleeding events or elevations in the International Normalized Ratio (INR) have been reported in some patients taking warfarin while on sorafenib therapy. Patients taking concomitant warfarin should be monitored weekly for changes in prothrombin time, INR or clinical bleeding episodes.

****Bone marrow exam should be performed at Screening the end of Cycle 1, every 2-3 cycles for the first year, then at the discretion of the treating physician. Any change to this schedule that the treating physician feels is in the best interest of the patient must be approved by the PI.

Molecular studies (FLT3 and NPM1) performed at baseline only and on patients with unknown status.

***** Labs will be collected once weekly for the first 2 cycles, then monthly thereafter (differential can be omitted if WBC is $\leq 0.5 \times 10^9/L$)

*****Any tumor masses will be measured before and after the treatment to assess their response to treatment.

4.2.1 Patients will be treated according to the following schedule:

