Hypertension is a known and potentially serious adverse event associated with Sorafenib treatment. Patients will have their blood pressure monitored and recorded weekly during the first cycle of therapy, either at the doctor's office or by using any calibrated electronic device (such as those found at a local drug store or pharmacy). Patients will have a Blood Pressure Diary on which to record the measurements, which will be kept with research chart. If the patient's blood

pressure is sustained at an elevated level at any time (>150/100), they should contact their treating physician.

Blood pressure measurements considered out of the normal range are diastolic pressure > 90 mm Hg and/or systolic pressure > 150 mm Hg, or a 20 mm Hg increase in diastolic pressure if the previous measurement was within normal limits.

The dose-modification schedule to be followed in the event of treatment-induced hypertension is outlined in Table 3. **The choice of anti-hypertensive medication to be used in cases of treatment-induced hypertension will be at the investigator's discretion and based on site-specific treatment guidelines as applicable.** All anti-hypertensive medications used for the management of treatment-emergent hypertension should be recorded in the subject's eCRF.

Table 3 Dose Modifications of Sorafenib for Hypertension

Grade (CTCAE v4.0)	Antihypertensive Therapy	Blood Pressure Monitoring	Sorafenib Dose
Grade 1 Pre-hypertension (systolic BP 120-139 mm Hg or diastolic BP 80-89 mm Hg)	None	Consider increased BP monitoring	No change
Grade 2 (asymptomatic) systolic BP 140-159 mm Hg or diastolic BP 90-99 mm Hg	Begin anti-hypertensive therapy as prescribed by the investigator based on site-specific treatment guidelines as applicable.	Increase frequency and monitor (by health professional) every 2 days until stabilized	No change
Grade 2 recurrent or persistent (> 24 hrs); symptomatic increase by 20 mm Hg(diastolic)/ OR Diastolic BP > 90 mm Hg and systolic > 140 mm Hg if previously WNL OR Grade 3	Add agent(s): as prescribed by the investigator based on site-specific treatment guidelines as applicable	Increase frequency and monitor (by health professional) every 2 days until stabilized; continue qod monitoring to stabilization after dosing restarted.	Hold ^a Sorafenib until symptoms resolve and diastolic BP < 90 mm/Hg. Resume treatment at 1 dose level lower ^b . If diastolic not controlled (< 90) on therapy, reduce another dose level ^c

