Grade 4 Life Threatening			Off protocol therapy

- ^a Subjects requiring a delay of > 28 days should go off protocol therapy.
^b May be able to resume full dose later once blood pressure is adequately controlled.
^c Subjects requiring > 2 dose reductions should go off protocol therapy.

CTCAE v4.0 definitions

Grade 1: Prehypertension (systolic BP 120-139 mm Hg or diastolic BP 80-89 mm Hg)
Grade 2: Stage 1 HTN (systolic 140-159 mm Hg or diastolic BP 90-99Hg, medical intervention indicated; recurrent or persistent (>24 hrs) or symptomatic increase by >20 mmHg (diastolic) or to > 140/90if previously WNL; monotherapy indicated.
Grade 3: Stage 2 HTN (systolic BP > = 160 mm Hg or diastolic BP > = 100 mm Hg): medical intervention indicated; requiring more than one drug or more intensive therapy than previously
Grade 4: life threatening (e.g., malignant hypertension, transient or permanent neurologic deficit, hypertensive crisis)

Patients who develop GI perforation should discontinue therapy and be taken off study.

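### The limit at which patients are told to call about blood pressure (sustained >150/100) lies above the pressures at which Table 3 starts treatment and closer checks

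*Combined protocol and SAP*

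**What the plan says.** Three sets of limits stand close together in the Hypertension part of section 5.

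- **Patient call.** Patients are to call if their blood "pressure is sustained at an elevated level at any time (>150/100), they should contact their treating physician". First-cycle readings are weekly and may be taken at the office or on an electronic device the patient uses; they go into a diary.
- **Out-of-range definition.** "Blood pressure measurements considered out of the normal range are diastolic pressure > 90 mm Hg and/or systolic pressure > 150 mm Hg". A diastolic rise of 20 mm Hg from normal also counts. No patient instruction is attached to it.
- **Table 3.** Row 2 covers "Grade 2 (asymptomatic) systolic BP 140-159 mm Hg or diastolic BP 90-99 mm Hg": begin antihypertensive therapy, leave sorafenib unchanged, and "Increase frequency and monitor (by health professional) every 2 days until stabilized". Row 3 opens with "Grade 2 recurrent or persistent (> 24 hrs", goes on to symptomatic rises and ends with grade 3. Its actions are to add agents and "Hold ^a Sorafenib until symptoms resolve" and diastolic pressure is below 90, then resume one dose level lower. The definitions under the table give grade 3 as "Stage 2 HTN (systolic BP > = 160 mm Hg or diastolic BP > = 100 mm Hg".

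The calendar footnote in section 4.2 adds: "Blood pressure should be monitored weekly during the first 4 weeks of sorafenib therapy". After that, monitoring follows standard practice, with a check before each cycle.

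**The concern.** The call sentence is the only trigger in the hypertension text that the patient initiates. Where a reading is taken outside the clinic, it decides whether the physician hears of the reading before the next visit. If its limit is above the level at which the protocol wants treatment to begin, a patient can follow the instruction exactly and still have a pressure that Table 3 says should be treated and rechecked every 2 days. The section itself describes hypertension on sorafenib as a known and potentially serious event. What is at stake is prompt treatment and monitoring of individual patients. Section 13's sample size, power and stopping boundaries do not depend on this sentence.

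**Working it through.** The plan states no figure to reproduce. The check sets the limits against each other.

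**Inputs** (all from section 5, Hypertension text, Table 3 and the definitions beneath it)

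- Grade 3: systolic >=160 or diastolic >=100.
- Grade 2: not grade 3, and systolic 140-159 or diastolic 90-99.
- Call, either value enough: systolic >150 or diastolic >100.
- Call, both values needed: systolic >150 and diastolic >100.
- Out of range: diastolic >90 and/or systolic >150. The 20 mm Hg rise is left out because it needs an earlier reading.

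**Gap between call limit and treatment start:** 150 - 140 = 10 mm Hg systolic; 100 - 90 = 10 mm Hg diastolic.

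**Sustained readings, classified**

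| Reading | Grade | Call if either | Call if both | Out of range |
|---|---|---|---|---|
| 145/85 | 2 | no | no | no |
| 135/95 | 2 | no | no | yes |
| 148/96 | 2 | no | no | yes |
| 150/100 | 3 | no | no | yes |
| 155/95 | 2 | yes | no | yes |
| 165/95 | 3 | yes | no | yes |
| 148/105 | 3 | yes | no | yes |
| 151/101 | 3 | yes | yes | yes |

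**General result for grade 2.** Every grade 2 reading has diastolic 99 or less, so the diastolic part of the call limit is never met. If either value is enough, a call then depends only on systolic >150, and every grade 2 reading with systolic 150 or less is missed. If both are needed, every grade 2 reading is missed.

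**General result for grade 3.** If either value is enough, a miss requires systolic <=150 and diastolic <=100. With systolic that low, the reading is grade 3 only if diastolic is >=100, so only diastolic exactly 100 is left. This is the difference between >100 and >=100. If both are needed, every grade 3 reading with systolic <=150 or diastolic <=100 is missed.

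**Count as a check** (whole-number pairs, systolic 120-180 by diastolic 70-120)

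- Grade 2 pairs: 40 x 30 - 20 x 20 = 800. Missed if either is enough: 31 x 30 - 20 x 20 = 530. Missed if both are needed: 800.
- Grade 3 pairs: 61 x 51 - 40 x 30 = 1,911. Missed if either is enough: 31 (diastolic 100, systolic 120-150). Missed if both are needed: 1,911 - 30 x 20 = 1,311.

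The counts depend on the grid chosen. They describe how the limits overlap and do not measure risk.

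**The case against.** A call limit for patients and a dosing table for clinicians serve different purposes and need not be identical. The protocol calls its dose-modification tables recommendations and allows variation after discussion with the principal investigator. There are other routes to detection: weekly readings in the first 4 weeks, laboratory visits weekly for two cycles and monthly after that, azacitidine on 7 days of each cycle, and pre-cycle checks. The diary instructions are not in the document, so what patients are told in full is unknown. All of this stands and limits the weight of the point. It does not explain why a sustained pressure that needs treatment under Table 3 should not prompt a call.

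Three stronger readings are tempting, and the documents do not support them.

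- **That a sustained 148/96 plainly calls for a sorafenib hold.** Row 3 does list grade 2 lasting more than 24 hours apart from the symptomatic rise. But it speaks of adding agents, which suggests that treatment has begun, and it ties the hold to symptoms resolving. The section 4.2 footnote considers stopping sorafenib for severe or persistent hypertension despite antihypertensive therapy. Row 2's first recheck also comes at 2 days; if 24 hours of untreated grade 2 forced a hold, row 2 would hardly ever apply. The hold is ambiguous for a first asymptomatic episode.
- **That grade 3 pressures are widely missed.** This needs the both-values reading. The neighbouring out-of-range sentence uses and/or, and the grade definitions use or, which favours the either-value reading. The gap is then a single diastolic value.
- **That the gap matters most over the long period after week 4.** The call applies at any time, but home readings are asked for only in cycle 1. After that it acts only on readings a patient chooses to take.

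**Conclusion.** The mismatch is real and small. On either reading of the call sentence, sustained grade 2 pressures with systolic 150 or less, and grade 3 pressures with diastolic exactly 100 and systolic 150 or less, lead to no call, although Table 3 asks for action at these pressures. If both values are needed, no grade 2 pressure and only some grade 3 pressures lead to one.

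The main consequence is a delayed start of antihypertensive therapy and of the 2-day checks, for readings away from the clinic and mostly in cycle 1. No number of affected patients can be given. Section 2.1 reports hypertension in 35% of patients in the phase I sorafenib studies, but that is not a rate of persistent grade 2 pressure on this combination.

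The conclusion rests on the protocol sentence alone and assumes that the diary, which is not in the document, sets no lower limit. It should be handled as a minor safety clarification.

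**What to change.** Rewrite the call sentence so that:

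- patients call for sustained systolic >=140 or diastolic >=90, with either value sufficient;
- patients who enter with systolic 140-150 or diastolic 90, which section 3.2 allows, call for a sustained rise above a limit that the treating physician records at baseline;
- all patients call at systolic >=160 or diastolic >=100.

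The out-of-range definition can stay as it is, because its limits of 150 and 90 match the eligibility limit in section 3.2. Row 3 of Table 3 should be reworded only if the clinical team confirms whether a first asymptomatic grade 2 episode lasting more than 24 hours is meant to hold sorafenib.

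The cost is a short clarifying amendment, a place to record the individual limit (the diary would do), agreement with any diary instruction that repeats the limit, and some extra patient calls.

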Females of childbearing potential: Recommendation is for 2 effective contraceptive methods during the study. Adequate forms of contraception are double-barrier methods (condoms with spermicidal jelly or foam and diaphragm with spermicidal jelly or foam), oral, depo provera, or injectable contraceptives, intrauterine devices, and tubal ligation.

Male patients with female partners who are of childbearing potential:

Recommendation is for male and partner to use at least 2 effective contraceptive methods, as described above, during the study.

8. Ability to understand and the willingness to sign a written informed consent. A signed informed consent must be obtained prior to any study specific procedures.
9. $INR \leq 1.5$. Patients receiving anti-coagulation treatment with an agent such as warfarin or heparin **may** be allowed to participate. For patients on warfarin, the INR should be measured prior to initiation of sorafenib and monitored weekly, or as defined by the local standard of care, until INR is stable.

3.2 Exclusion criteria:

- ◆ Nursing and pregnant females.
- ◆ Patients with acute promyelocytic leukemia are excluded
- ◆ Patients with known allergy to sorafenib or azacitidine, mannitol or any of their components.
- ◆ Patients with known severe impairment of gastrointestinal (GI) function or GI disease that may significantly alter the absorption of sorafenib.
- ◆ Patients with any other known disease (except carcinoma in-situ) or concurrent severe and/or uncontrolled medical condition (e.g. uncontrolled diabetes, cardiovascular disease including congestive heart failure, myocardial infarction

within 6 months and uncontrolled hypertension, chronic renal disease (creatinine clearance < 20 ml/min using the Cockcroft and Gault formula), or active uncontrolled infection) which could compromise participation in the study.

- ◆ Patients with a known confirmed diagnosis of HIV infection or active viral hepatitis (B or C).
- ◆ Patients who have had any major surgical procedure within 28 days prior to Day 1.
- ◆ Patients unwilling or unable to comply with the protocol.
- ◆ Cardiac disease: Congestive heart failure > class II NYHA. Patients must not have unstable angina (anginal symptoms at rest) or new onset angina (began within the last 3 months) or myocardial infarction within the past 6 months.
- ◆ Uncontrolled hypertension defined as systolic blood pressure > 150 mmHg or diastolic pressure > 90 mmHg, despite optimal medical management.

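### Table 3 holds sorafenib for systolic or diastolic hypertension but names only diastolic pressure in its release and control tests, which conflicts with the protocol's grade 1 restart rules

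*Combined protocol and SAP*

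**What the plan says.** All references are to the combined protocol and SAP.

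**Into the hold.** The CTCAE definitions printed under Table 3 grade hypertension on either component: "Grade 3: Stage 2 HTN (systolic BP > = 160 mm Hg or diastolic BP > = 100 mm Hg". The hold row of Table 3 covers recurrent, persistent or symptomatic grade 2 and ends with "Diastolic BP > 90 mm Hg and systolic > 140 mm Hg if previously WNL OR Grade 3".

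**Out of the hold.** The same row says to hold "Sorafenib until symptoms resolve and diastolic BP < 90 mm/Hg", then to restart one dose level lower. After restart it adds: "If diastolic not controlled (< 90) on therapy, reduce another dose level". No systolic value stands in either sentence.

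**Which table applies.** The Hypertension text of Section 5 states: "The dose-modification schedule to be followed in the event of treatment-induced hypertension is outlined in Table 3".

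**General restart rules.** Section 4.2.1 restarts sorafenib after a sorafenib-related toxicity once it is back to grade 1 or baseline. The first table of Section 5.0 (non-hematological grade 3 or 4, and persistent grade 2 judged clinically significant) and Table 2 (non-hematologic grade 3) require recovery to grade 1 or less.

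**Systolic pressure elsewhere.** The paragraph above Table 3 treats systolic pressure above 150 mm Hg as out of range. Section 3.2 excludes patients with "Uncontrolled hypertension defined as systolic blood pressure > 150 mmHg or diastolic pressure > 90 mmHg, despite optimal medical management".

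**The concern.** A hold rule needs an exit test that speaks to the reason for the hold. Here a patient can enter on systolic pressure, but the only pressure checked on the way out is diastolic. When diastolic pressure is already below 90 and there are no symptoms, Table 3 gives the hold no duration, while the general rules keep the patient off sorafenib until systolic pressure has also come down. A treating physician asking whether such a patient may restart gets two different written answers.

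What is at stake is sorafenib exposure, and how a toxicity that the protocol itself calls known and potentially serious is handled. Sorafenib is given continuously, so the question can arise at any point in treatment.

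**Working it through.** The protocol states no figure for this point, so the check is to apply its own rules to example readings.

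**Inputs**
- Grades (definitions under Table 3): grade 3 if systolic ≥160 or diastolic ≥100; grade 2 if systolic 140–159 or diastolic 90–99; grade 1 if systolic 120–139 or diastolic 80–89. A reading is given the highest grade that either component reaches. It follows that grade 1 or less means systolic ≤139 and diastolic ≤89.
- Table 3 release: no symptoms and diastolic <90.
- General restart (Section 5.0 table, Table 2): grade ≤1. Section 4.2.1 adds baseline as an alternative.

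**Results for an asymptomatic patient**

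| Reading (mm Hg) | Grade | Table 3 release met? | Grade ≤1 met? |
|---|---|---|---|
| 160/75 | 3 | yes | no |
| 160/89 | 3 | yes | no |
| 170/85 | 3 | yes | no |
| 175/85 | 3 | yes | no |
| 160/90 | 3 | no | no |
| 165/95 | 3 | no | no |
| 165/99 | 3 | no | no |
| 150/105 | 3 | no | no |
| 150/85, held as recurrent or persistent grade 2 | 2 | yes | no |
| 139/89 | 1 | yes | yes |

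**Reading the table**
1. In the first four rows systolic pressure is ≥160 and diastolic <90. The reading that starts the hold already satisfies the condition that ends it, but it fails the grade ≤1 rule.
2. At 160/90, 165/95 and 165/99 the grade also comes from systolic pressure alone, but diastolic pressure is not below 90, so release is not met. The effect needs diastolic <90.
3. With symptoms, no reading meets the release condition until they resolve.
4. The 150/85 row shows the same effect for held grade 2. The conflict there is with Section 4.2.1 and with the persistent grade 2 row of the Section 5.0 table (where the event is judged clinically significant). Table 2 sets a restart condition only for grade 3.
5. After restart, a patient still at 170/85 passes the control test, because 85 is below 90, so that sentence calls for no further reduction. Yet the reading is again grade 3, which belongs in the hold row. Table 3 itself therefore points two ways.

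**The case against.** The strongest defence is that Table 3 is the specific schedule for hypertension and so overrides the general rules, that entry and exit tests need not mirror each other, and that the patient is protected in other ways. The hold row also calls for added antihypertensive treatment, checks by a health professional every two days until stable, and restart one level lower. A footnote to the study calendar in Section 4.2 says that stopping sorafenib, for a time or for good, should be considered for severe or persistent hypertension despite treatment, and it is not limited to diastolic pressure. The PI may also approve departures from the schedule.

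Much of this stands. It rules out several stronger readings that a reader might infer:
- *That Table 3 does nothing for systolic events.* It does not say that. Only the length of the hold and the later control test lack a systolic criterion.
- *That systolic pressure could never lead to further reductions or to leaving therapy.* A repeat systolic grade 3 reading re-enters the row, and Table 3's limit of two reductions can be reached that way.
- *That the toxicity stopping rule in Section 13.2 is distorted.* A reading of 170/85 is grade 3 however the hold ends, so the event is already available to be counted.
- *That sites will diverge.* Section 14.1 speaks of a single study center.
- *That patients restart at a pressure that would have barred entry.* The exclusion applies despite optimal management, and a first on-treatment reading is not shown to meet it.
- *That the number affected can be estimated.* Section 2.1 gives hypertension in 35% in the phase I studies, with no split by grade or component. Grade 1 and first asymptomatic grade 2 readings cause no hold.

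What the defence does not remove is the conflict. The protocol does not say that Table 3 displaces the grade ≤1 rules. Footnote b of Table 3, "May be able to resume full dose later once blood pressure is adequately controlled", concerns a later return to full dose, not the end of the hold. Discretion to depart from a rule does not settle which rule is the default.

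**Conclusion.** The point holds in a limited form. For an asymptomatic patient with systolic pressure ≥160 and diastolic <90, Table 3's release condition is met at the triggering reading. The Section 5.0 table and Table 2 do not permit restart at that reading, and neither does Section 4.2.1 unless that level is the patient's baseline. The same mismatch affects recurrent or persistent grade 2 held with diastolic pressure below 90, within the limits given in the working.

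This rests on two assumptions: that a reading takes the highest grade either component reaches, and that the general restart rules apply to hypertension unless the protocol says otherwise. If Table 3 were declared to override them, the conflict between sections would go. The mismatch inside Table 3, between a two-component trigger and diastolic-only pressure tests, would remain.

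The defect is one of clarity in a safety rule. It should be corrected, but it has no bearing on sample size, power or error rates, and the documents give no basis for a count of affected patients.

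**What to change.** Reconcile the hold-release and control conditions in Table 3 with the grade definitions printed beneath it and with the restart rules in Section 4.2.1, the Section 5.0 table and Table 2. State explicitly which rule governs treatment-induced hypertension. The pressure values and the form of the rule are for the sponsor's clinicians to set, and this review takes no view on them.

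The cost is a short protocol amendment: one cell of Table 3 and a sentence on precedence. Both components of blood pressure already enter the protocol's grading, so no visit or measurement is added.
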